5.2.4 Neuropsychiatric Inventory – Clinician Rating Scale (NPI-C)

The complete NPI-C, which include agitation and aggression domains, will be administered at Baseline and Weeks 12/ET visits while only the NPI-C agitation and aggression domains will be administered at all other visits, i.e. Screening, and Weeks 2, 4, and 8 visits.

The NPI-C is a scale to assess the 14 neuropsychiatric symptoms (domains) in patients with dementia. For each domain, there are three NPI-C sections: caregiver interview, patient interview and clinician rating. The caregiver interview includes the frequency (0-4), severity (0-3) and distress (0-5) scores. The subject interview consists of the subject-reported frequency score (0-4). The clinician rating is a clinical impression severity score (0-3) based on all available interview information. For the caregiver interview, if a response of 0 is selected for the frequency score, then the severity and distress scores will be set to 0. For each domain, the domain score is the sum of the clinical impression severity scores within each domain, with higher scores denoting more serious symptoms. Before deriving any combined domain scores, if there are any missing items, the individual domain score will be imputed as follows:

For the delusions, hallucinations, aggression, elation/euphoria, aberrant motor disturbance, sleep disorders, appetite and eating disorders, and aberrant vocalizations domains, if only

1 item is missing then the respective domain score will be imputed by replacing the missing item with the mean of the non-missing items (rounded to the nearest integer) for that subject and timepoint within the domain. If more than 1 item is missing then the respective domain score will be missing.

For the agitation, dysphoria, anxiety, apathy/indifference, and irritability/lability domains, if up to 2 items are missing then the respective domain score will be imputed by replacing each missing item with the mean of the non-missing items (rounded to the nearest integer) for that subject and timepoint within the domain. If more than 2 items are missing then the respective domain score will be missing.

For the disinhibition domain, if up to 3 items are missing then the respective domain score will be imputed by replacing each missing item with the mean of the non-missing values (rounded to the nearest integer) for that subject and timepoint within the domain. If more than 3 items are missing then the respective domain score will be missing.

Table 3 NPI-C Domain Score

NPI-C Domain	# items	Domain Score Range	Maximum Missing Items Allowed for Deriving the Domain Score*
Delusions	8	0 – 24	1
Hallucinations	7	0 – 21	1
Agitation	13	0 – 39	2
Aggression	8	0 – 24	1
Dysphoria	13	0 – 39	2
Anxiety	14	0 – 42	2
Elation/Euphoria	6	0 – 18	1
Apathy/Indifference	11	0 – 33	2
Disinhibition	16	0 – 48	3
Irritability/Lability	12	0 – 36	2
Aberrant Motor Disturbance	9	0 – 27	1
Sleep Disorders	8	0 – 24	1
Appetite and Eating Disorders	9	0 – 27	1
Aberrant Vocalizations	8	0 – 24	1

* For each domain, the maximum number of missing items allowed for deriving the domain score is the nearest integer to but $\leq 20\%$ of the total items in that domain. If there are any missing items, the individual domain score will be imputed first before calculating the combined domain scores.

The NPI-C combined agitation and aggression domain score is calculated as the sum of the agitation domain score and the aggression domain score. If either the agitation or aggression domain score is missing, the NPI-C combined agitation and aggression domain score will be missing.

The NPI-C combined delusions and hallucinations domain score is calculated as the sum of the delusions domain score and the hallucinations domain score. If either the delusions or hallucinations domain score is missing, the NPI-C combined delusions and hallucinations domain score will be missing.

The NPI-C combined dysphoria and apathy/indifference domain score is calculated as the sum of the dysphoria domain score and the apathy/indifference domain score. If either the dysphoria or apathy/indifference domain score is missing, the NPI-C combined dysphoria and apathy/indifference domain score will be missing.

The NPI-C total score is calculated as the sum of all 14 individual domain scores. The NPI-C total score ranges from 0 to 426, with higher scores denoting more serious symptoms. After applying the preceding data handling rules, if any of the domain scores remain missing, the total score will be missing.

5.2.5 Modified Alzheimer's Disease Cooperative Study – Clinical Global Impression-Change (mADCS-CGIC)

The mADCS-CGIC is assessed at Baseline, Weeks 2, 4, 8 and 12/ET visits.

The mADCS-CGIC scale will be used to allow the Investigator to determine the subject's overall clinical condition as it relates to their symptoms of agitation and aggression, and to address the clinical significance of changes from Baseline in other psychometric measures. The mADCS-CGIC interview will be performed by the Investigator or a medically qualified rater. After completion of the interview, the rater will be asked to rate the subject's symptoms of agitation and aggression relative to the Baseline interview, using a standardized 7-point scale (1 = marked improvement to 7 = marked worsening). Higher scores denote worsening or less improvement in agitation and aggression symptoms.

Missing mADCS-CGIC scores will not be imputed.

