### **6.1.3 Neuropsychiatric Inventory – Clinician Rating Scale (NPI-C)**

The NPI-C was developed to assess psychopathology in patients with dementia (de Medeiros et al. 2010; see [Appendix G](#)). The NPI-C evaluates NPS across many domains, as in the NPI (Cummings et al. 1994), as a standalone measure for specific NPS domains (e.g., dysphoria, agitation), or as a combination of both (presence of NPS across domains plus particular focus on one or more specific domains). The score of each item, if present, is clinically evaluated based on the symptom frequency, severity/intensity, and distress of a behavior. Multiple behaviors within a category are rated and included in the score. The NPI-C version of the NPI scale was designed to be administered by the clinician to the caregiver and can be administered to a professional caregiver or other involved person as long as they have detailed knowledge of the subject's behavior. If a subject is not able to provide reliable information (e.g., due to cognitive impairment, or is uncooperative), the NPI-C should be rated by the clinician using all other available information including behavioral observations.

The complete NPI-C, which includes agitation and aggression domains, will be administered by a qualified rater at Baseline (Day 1) and at Weeks 12 (EOS/ET) and the NPI-C agitation and aggression domains will be administered at Screening, and at Weeks 2, 4, and 8.

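### The NPI-C zero-fill rule in SAP 5.2.4 acts on fields that are never scored; a blank clinician rating for an absent behaviour is mean-imputed or makes the domain missing

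*SAP*

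**What the plan says.** SAP 5.2.4 splits each NPI-C domain into a caregiver interview, a patient interview and a clinician rating.

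- **Caregiver fields:** "The caregiver interview includes the frequency (0-4), severity (0-3) and distress (0-5) scores".
- **Clinician field:** "The clinician rating is a clinical impression severity score (0-3) based on all available interview information".
- **Zero rule (caregiver interview only, by its opening words):** "if a response of 0 is selected for the frequency score, then the severity and distress scores will be set to 0".
- **What is scored:** "the domain score is the sum of the clinical impression severity scores within each domain".
- **Missing items:** for five domains including agitation, "if up to 2 items are missing then the respective domain score will be imputed by replacing each missing item with the mean" (taken over the rated items and rounded to an integer). Aggression and seven other domains allow one missing item, and disinhibition allows three. Beyond the limit the domain is missing. A missing domain makes any combined score that uses it missing, and also the NPI-C total.

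Protocol 6.1.3 describes the rating in these words: "The score of each item, if present, is clinically evaluated based on the symptom frequency, severity/intensity, and distress of a behavior".

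**The concern.** The SAP foresees that fields may be empty after a frequency of 0, but fills two fields that feed no endpoint. The field that feeds every NPI-C endpoint is left to the general missing-item rule. That rule can give a positive severity to a behaviour the caregiver reported as not occurring. The ADCS-ADL section (SAP 5.2.3) avoids this: a NO or DON'T KNOW answer sets the scored item itself to 0 before missing-item handling starts.

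Three uses of the scores would be affected:

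- **Responder analyses (SAP 13.4).** These are also run with missing counted as non-response. A subject whose agitation behaviours are all absent, with three ratings left blank, would count as a non-responder even for the 100% reduction criterion.
- **NPI-C total and the domains other than agitation and aggression (SAP 13.3).** A missing Week 12 value takes the previous value, Baseline included. The full NPI-C is given only at Baseline and Week 12/ET, so a lost score normally becomes a change of zero. An observed-case summary is presented alongside.
- **The Baseline subgroup cut of <22 or ≥22 (SAP 12.5).** This cut is applied to the primary and secondary endpoints.

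**Working it through.** **1. Which field is scored.** If only the 0–3 clinician rating is summed, each domain maximum is 3 × items. Table 3 lists 14 domains with 142 items in all: 3 × 142 = 426, the total stated in SAP 5.2.4. All 14 domain maxima reproduce, as do all 14 missing-item limits (20% of items, rounded down). Caregiver severity and distress therefore enter no score.

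**2. Single records under the SAP rule.** The item patterns are assumed. Score = sum of rated items + blanks × rounded mean of rated items.

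| Domain | Rated items, sum | Blanks at frequency 0 | SAP score | Blanks as 0 |
|---|---|---|---|---|
| Agitation (13 items) | 11, sum 5 (mean 0.45 → 0) | 2 | 5 | 5 |
| Agitation | 11, sum 15 (mean 1.36 → 1) | 2 | 17 | 15 |
| Agitation | 11, sum 17 (mean 1.55 → 2) | 2 | 21 | 17 |
| Agitation | any | 3 | missing | sum stands |
| Aggression (8 items) | 7, sum 7 (mean 1 → 1) | 1 | 8 | 7 |
| Aggression | any | 2 | missing | sum stands |

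No inflation arises when the rated mean is below 0.5. The most that can be added to the combined score (range 0–63) is 3 × (2 + 1) = 9 points. A record can cross the subgroup cut: agitation sum 13 with 2 blanks gives 13 + 2 = 15, and aggression sum 6 with 1 blank gives 6 + 1 = 7. The combined score is then 22 instead of 19.

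**3. Loss of the combined score.** The documents give no blank rate, so a range is assumed. Let p = (share of items absent) × (share of absent items left blank), independent across items. Then P(missing) = 1 − P(Bin(13, p) ≤ 2) × P(Bin(8, p) ≤ 1).

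- Half absent, 2% blank (p = 0.01): 1 − 0.9997 × 0.9973 = 0.3%
- Half absent, 5% blank (p = 0.025): 1 − 0.9963 × 0.9842 = 2%
- Half absent, 10% blank (p = 0.05): 1 − 0.9755 × 0.9428 = 8%
- 70% absent, 10% blank (p = 0.07): 1 − 0.9422 × 0.8965 = about 15.5%

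The same product over all 14 domains gives a missing NPI-C total in about 2%, 13% and 44% of visits for the first three cases.

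**4. Inflation of the combined score.** This was simulated with 200,000 visit records. Severities of present items were 1, 2 or 3 with probability 0.45, 0.40 and 0.15 (assumed). With half of items absent and 2%, 5% or 10% of those blank, about 17%, 36% and 54% of records are inflated, by a mean of 1.1 to 1.4 points.

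**5. Does the effect track improvement?** At 10% blank:

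| Share of items absent | 30% | 50% | 70% | 85% |
|---|---|---|---|---|
| Mean inflation, non-missing scores (points) | 0.69 | 0.83 | 0.64 | 0.23 |
| Combined score missing | 3% | 8% | about 15% | 22% |

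A move from 30% to 50% absent understates improvement by about 0.83 − 0.69 = 0.14 points. A move from 50% to 70% overstates it by about 0.83 − 0.64 = 0.19 points. Loss of scores rises throughout.

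**The case against.** The strongest objection is that the blanks are hypothetical. Protocol 8.1 requires sites to supply every requested eCRF entry and to account for gaps, and monitors raise queries. The clinician scale includes 0, so absence has a value that can be recorded. A reader might infer from the words in Protocol 6.1.3 about an item being present that raters are told to skip absent behaviours. The text does not say so: it describes what the rating is based on. The NPI-C form (Protocol Appendix G) is not in the text available, so neither a forced entry nor an optional one can be shown. This objection stands, and it makes the point conditional.

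A reader might also infer that improved visits are systematically scored too high, because improvement brings more absent items. Step 5 does not support that. The imputed mean falls as subjects improve, Baseline is inflated as well, and the net shift in change can take either sign. Only the loss of scores moves in one direction.

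It is also tempting to count every record with an imputed blank as inflated. With half of items absent, that share is P(not missing) − (1 − p)^21: 0.997 − 0.810 = 19%, 0.980 − 0.588 = 39% and 0.920 − 0.341 = 58%. Some of those blanks are imputed as 0, so the inflated shares are the lower figures in step 4.

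In the SAP's defence, the severity it sets to 0 might be read to include the clinician's. The sentence is confined to the caregiver interview, so that reading fails.

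**Conclusion.** The gap in the rule is real and follows from the SAP text alone. A clinician rating left blank at caregiver frequency 0 is scored as the rounded mean of the other items, or removes the domain and every score built on it. How much this matters is unknown: it is nil if the eCRF forces an entry. All rates in steps 3 to 5 rest on the assumed shares of absent and blank items, independence across items, and the assumed severities. On those assumptions inflation is common but small, and its net effect on change from Baseline is at most about 0.2 points in the moves examined. The loss of scores is the more serious part, because it rises as behaviours resolve and then feeds non-response imputation and LOCF from Baseline.

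The reach is limited to the exploratory NPI-C endpoints, the NPI-C responder analyses and the <22 / ≥22 subgroup. CMAI and ZBI scores are not touched, and no hypothesis testing is planned. This is a minor point, worth correcting because the correction is cheap.

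**What to change.** In SAP 5.2.4, before the missing-item rule, add: a blank clinical impression severity is set to 0 when the caregiver frequency for that item is 0 and the subject frequency is 0 or was not obtained. Apply mean imputation and the missing-item limits only to blanks that remain. Any recorded clinician rating stands, whatever the frequencies.

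The cost is one sentence and one derivation line, using fields already collected. If every clinician item is mandatory in the eCRF, the rule changes nothing, and the SAP could simply say so. The downside is that the clinician rating draws on all interview information: a clinician who would have rated above 0 but left the field blank is scored 0. The documents do not show how often that would occur.

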5.2.6 Karolinska Sleepiness Scale (KSS)

KSS is assessed at Baseline, Weeks 2, 4, 8 and 12/ET visits.

The KSS is a self-reported subjective measure of a subject's level of drowsiness. With the modified version, respondents must choose which of nine statements (1 = extremely alert to 9 = very sleepy, great effort to keep awake, fighting sleep) most accurately describes their level of sleepiness over a period of time, which for this study will be “on average over the previous week”. Higher scores denote more drowsiness.

Missing KSS scores will not be imputed.

5.2.7 Mini-Mental State Examination (MMSE)

MMSE is assessed at Screening, Baseline, Weeks 4, 8 and 12/ET visits.

The MMSE is an 11-area, 30 items questionnaire that is used to measure cognitive impairment, with lower scores indicating more severe cognitive impairment.

The total score (0-30) is calculated as the sum of the 30 item scores. If there are less than or equal to 6 missing items then the total score will be imputed as the mean of the non-missing values multiplied by 30 and rounded to the nearest integer for that subject and timepoint. If there are more than 6 missing items then the total score will be missing.

5.2.8 Global Clinician Assessment of Suicidality (GCAS)

Global Clinician Assessment of Suicidality (GCAS) is assessed at Screening, Baseline, Weeks 2, 4, 8, 12/ET and Follow-up (if applicable) visits.

The GCAS will be used to assess the occurrence of treatment-emergent suicidal ideation and behavior. The GCAS is a clinician-rated, 5-point scale (0–4) that is designed to rate the subject's suicidality based on the report of the subject, the report of the study partner/caregiver, and the clinician's global assessment. Ratings can be 0 (“Absent”), 1 (“Feels life is not worth living”), 2 (“Wishes he/she were dead or any thoughts of possible death to self”), 3 (“Suicidal ideas or gesture”), or 4 (“Attempt at suicide”). The Investigator will record a subject rating, a partner/caregiver rating, and a clinician rating. For a rating of 3 or 4 based on the clinician's assessment, the date of event will be recorded. At Screening visit lifetime suicidality and suicidality for the past 3 months will be assessed, at all other visits suicidality since the previous visit will be assessed.

Missing GCAS scores will not be imputed.

5.3 Analysis Visit Windows

Baseline will be defined as the last non-missing result, including results from repeated and unscheduled measurements, before dosing.

Efficacy, safety, and PK assessments will be summarized by analysis visit as presented in Table 4 below.

Table 4 Analysis Visit Windows

Analysis Visit Name	Target Study Day ¹	Study Day Interval
Baseline	1	≤ 1
Week 2	15	2 to 21
Week 4	29	22 to 42
Week 8	57	43 to 70
Week 12	85	71 to 99
Follow-up	115	≥ 100

¹ study day = assessment date - first dose date + 1 if the assessment date \geq first dose date, otherwise study day = assessment date - first dose date. Study day 1 is the day of first administration of study drug (pimavanserin or placebo).

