### **3.2.7 30-day Safety Follow-up (Telephone; Week 16)**

- Assessment of concomitant medications/treatments
- Assessment of AEs
- GCAS

Note: A 30-day safety follow-up is to be completed for those subjects who discontinue prematurely from the study or who do not enroll in the open-label extension study.

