- a. Study visits are designated by weeks and have a ± 3 -day window (Visits 2 through 5) or a $+7$ -day window (Visit 6) calculated from the Baseline Visit (Day 1). Clinic visits may be split over multiple days within the specified windows, if necessary.
- b. The screening period must be at least 2 weeks long and no more than 4 weeks long.
- c. For subjects who discontinue prematurely from the study or who do not enroll in the open-label extension study, a follow-up safety assessment will be conducted by telephone call approximately 30 days after the last dose of study drug.
- d. NPI-C combined agitation and aggression domain score and wash-out of prohibited medications are the only eligibility assessments required at both Screening and Baseline (Day 1). All other eligibility criteria are to be established during Screening.
- e. Height is assessed as part of the vital sign measurement only at the Screening Visit; weight will be assessed at every clinic visit as part of the vital sign measurements.
- f. 12-lead ECG to be completed in triplicate at screening and single read at subsequent visits. ECGs can be performed any time before blood sampling or at least 30 minutes after blood sampling during clinic visits.
- g. Urinalysis requirement not applicable to subjects who are unable to provide urine sample (e.g., incontinent subjects).
- h. A serum pregnancy test should be performed at the initial screening visit. A urine pregnancy test should be performed at Baseline (Day 1), Week 4, and Week 12 (EOS/ET) for female subjects of childbearing potential.
- i. Note: If collection at Week 2 does not occur, then collection should be attempted at Week 8.
- j. Only the agitation and aggression domain will be completed at the Screening Visit.
- k. MRI or CT must be obtained during or subsequent to diagnosis of probable AD, or during the screening period (prior to Baseline).
- l. Any untoward medical occurrence that occurs after signing the informed consent form (i.e., during the screening period) should be recorded as an adverse event, even if dosing has not begun.
- m. The first dose of study drug must be administered to the subject at the clinic only after all Baseline assessments are performed, including the blood sampling for PK assessment. If any Baseline assessments extend to an additional day, the first dose of study drug will be administered at completion of assessments on this day.

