5.1 General Data Reporting Conventions

For continuous variables, the following summary statistics will be provided: number of subjects, mean, standard error of the mean (SE), standard deviation (SD), minimum, maximum and median. Unless specified otherwise, means, medians, and confidence intervals (CIs) will be presented to one more decimal place than the raw data, and the standard deviations and standard errors will be presented to 2 more decimal places than the raw data. Unless specified otherwise, all confidence intervals will be 2-sided 95% confidence intervals.

For categorical variables, summaries will include the number and percentage of subjects in each category, using the number of subjects with non-missing values as the denominator for the percentages (unless otherwise specified). Categories with zero counts will not have zero percentages displayed. Percentages will be presented with 1 decimal place.

When converting number of days to months, it will be calculated by dividing the number of days by 365.25 and then multiplying by 12. When converting number of days to years, the number of days will be divided by 365.25.

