14.6 Other Safety Variables

14.6.1 Suicidal Ideation and Behavior

GCAS is assessed at Screening, Baseline, Weeks 2, 4, 8, 12/ET and Follow-up (if applicable) visits.

The number and percentage of subjects for each GCAS rating (0-4) based on clinician's assessment will be tabulated by treatment group and visit. The number and percentage of subjects reporting any post-Baseline GCAS score of 3 or 4 based on clinician's assessment will also be tabulated for each treatment group.

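### Table 4 counts days from first dose, so an early discontinuer's follow-up GCAS rating misses the Follow-up row and is windowed to Week 4, 8 or 12

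*SAP*

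**What the plan says.** SAP 5.3 applies one windowing rule to all data: "Efficacy, safety, and PK assessments will be summarized by analysis visit as presented in Table 4 below". The note to Table 4 sets the origin at first dose: "study day = assessment date - first dose date + 1" for assessments on or after that date. The post-baseline windows are Week 2, Days 2–21; Week 4, Days 22–42; Week 8, Days 43–70; Week 12, Days 71–99; and Follow-up, Day 100 onward with a target of Day 115.

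The telephone call has a different origin. Footnote c to SAP Table 1 says that "a follow-up safety assessment will be conducted by telephone call approximately 30 days after the last dose of study drug", and Protocol 3.1 and 7.1 time it the same way. Protocol 3.2.7 makes it mandatory for early leavers: "A 30-day safety follow-up is to be completed for those subjects who discontinue prematurely from the study", and also for those who do not enter the extension. Footnote a to the same SAP table disagrees, with a +7-day "window (Visit 6) calculated from the Baseline Visit (Day 1").

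The call includes GCAS. SAP 5.2.8 schedules the scale at Screening, Baseline and the Week 2, 4, 8, "12/ET and Follow-up (if applicable) visits". SAP 14.6.1 says ratings based on the clinician's "assessment will be tabulated by treatment group and visit". SAP 5.1 computes percentages "using the number of subjects with non-missing values as the denominator for the percentages", unless specified otherwise.

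SAP 5.3.1 makes scheduled, unscheduled and early-termination assessments all eligible for the by-visit summaries. SAP 5.3.2 picks the assessment nearest the target day when several share a window. Neither section sets the call aside.

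**The concern.** The Follow-up row fits a subject who takes drug to about Week 12 and is called a month later. It does not fit a subject who stops early, for whom the call is also required. That subject's call comes well before Day 100, so the stated rule sends the rating to a treatment-period row.

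Two things then go wrong in the by-visit GCAS table. The Week 4, 8 and 12 numerators and denominators can include subjects who stopped drug about a month earlier, with a rating that covers the time since their previous visit. The Follow-up row omits those same subjects, although it is where a reader would look for their post-treatment rating. Nothing in the table would show this.

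**Working it through.** **Inputs.** Window limits and targets: SAP Table 4. Call timing: about 30 days after last dose, SAP Table 1 footnote c. Visit 6 allowance: +7 days, footnote a. Let L be the study day of the last dose, so the call falls on Day L + g, with g = 30 as the stated gap.

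**1. The plan's own figure.** Week 12 target 85 + 30 = 115, which is Table 4's Follow-up target. The row was built for the 30-day call of a subject dosed to Week 12.

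**2. Which row the call falls in.** Subtract g from each window's upper limit to get the latest L that maps to it. For g = 30:
- Week 2: 21 − 30 is below 1, so it is never reached
- Week 4: 42 − 30 = 12
- Week 8: 70 − 30 = 40
- Week 12: 99 − 30 = 69
- Follow-up: from 100 − 30 = 70

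Other gaps move the cuts. The 23- and 27-day gaps are illustrative readings of an approximate 30 days; 37 uses the +7-day allowance.

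| Gap g (days) | L giving Week 4 | L giving Week 8 | L giving Week 12 | L giving Follow-up |
|---|---|---|---|---|
| 23 | 1–19 | 20–47 | 48–76 | 77 or later |
| 27 | 1–15 | 16–43 | 44–72 | 73 or later |
| 30 | 1–12 | 13–40 | 41–69 | 70 or later |
| 37 | 1–5 | 6–33 | 34–62 | 63 or later |

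At g = 30, of the 85 possible last-dose days (1 to 85), 12 + 28 + 29 = 69 map to a Week 4, 8 or 12 window. This counts days, not subjects.

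**3. Example.** Last dose Day 28, call Day 28 + 30 = 58. This lies in Days 43–70, one day from the Week 8 target of 57, so the subject is counted at Week 8.

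**4. Completers.** Last dose on Days 82–88 puts the call on Days 112–118 at g = 30, and no later than Day 125 at g = 37. All reach Follow-up.

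**5. Competition with other ratings under SAP 5.3.2.**

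*Ratings taken on drug (day no later than L).* At g = 30, sharing the Week 4 window would need L ≥ 22 and L ≤ 12; Week 8, L ≥ 43 and L ≤ 40; Week 12, L ≥ 71 and L ≤ 69. None is possible, so the call never competes with an on-drug rating. The same holds at g = 37. With a shorter gap it can compete: at g = 27 for L = 43, 71 and 72 (3 days), and at g = 23 for L = 43–47 and 71–76 (11 days).

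*The early-termination (ET) visit after last dose.* The documents give no delay for this visit, so the delays below are assumed, with g = 30 and L = 1–69.

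| ET delay (days) | Call tabulated in a Week 4–12 row | Of these, displacing the ET rating | Call in no by-visit row |
|---|---|---|---|
| 0 or 1 | 69 | 0 | 0 |
| 7 | 64 | 6 | 5 (L = 39, 40, 67–69) |
| 14 | 53 | 14 | 16 |

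In no case does the call reach the Follow-up row.

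**The case against.** The best defence is that this is ordinary study-day windowing. No passage calls the Week 2–12 rows on-treatment rows, and SAP 5.3.1 puts early-termination visits into them on purpose. SAP 14.1 treats adverse events as treatment-emergent up to 30 days after last dose, so a call at that point sits at the edge of the plan's own treatment-emergent period. Nominal assignment has a cost too, because the Follow-up row would then mix different times since first dose. That would carry more weight if Table 4 had no Follow-up row. It has one, with a target equal to the 30-day call, and the rule misses it for the early discontinuers who must have the call.

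A second defence is that a rule may exist elsewhere. SAP 5.3.2 refers to a separate programming conventions document, SAP 1 puts table specifications in another document, and SAP 14.6.1 may mean nominal visit. These documents are not available here, so such a rule cannot be excluded. But SAP 5.3.2 cites the conventions in connection with multiple and incomplete assessments within a window, and SAP 5.3 states a general rule that gives the opposite result.

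Third, under footnote a, and the approximate Day 115 shown for Visit 6 in SAP Table 1, the call would land in Follow-up. That reading conflicts with footnote c and with the protocol, which time the call from last dose.

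Three limits do stand. The 69 of 85 days says nothing about how many subjects are affected, because last doses need not be spread evenly. A late early-termination visit can push the call out of the by-visit table altogether. And the consequence is small.

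**Conclusion.** The point holds as a minor error in the SAP as written. With a call 30 days after last dose, any subject whose last dose is before Day 70 has the follow-up GCAS rating windowed to Week 4, 8 or 12 and not to Follow-up. The cut moves to Day 63 for a call at 37 days and Day 77 at 23 days. This assumes that the call is timed from last dose and that no unseen specification overrides SAP 5.3. The number of subjects affected cannot be derived from the documents.

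Only the by-visit GCAS table is affected. The count of subjects with any post-baseline rating of 3 or 4 uses no windows, all assessments are listed, and no event is lost. Efficacy is untouched, because the call collects no efficacy scale. No hypothesis testing is planned.

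**What to change.** Add one sentence under Table 4 in SAP 5.3: the telephone follow-up (Visit 6) is assigned to the Follow-up row by nominal visit, whatever its study day, and is not eligible for the Week 2 to Week 12 rows. Reconcile footnotes a and c of the schedule, in both the SAP and the protocol, so that Visit 6 has one stated time origin.

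The cost is that sentence and a small programming change; no new data are needed. The Follow-up row will then cover varying times since first dose, which a table footnote can state.
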